2.0 OBJECTIVES

The aims of this 2-group, prospective, randomized controlled design are:

Aim 1: Evaluate the effect of a CG intervention, as compared to a control group, on CG primary (anxiety) and secondary (depression, HRQOL, and fatigue) outcomes.

Aim 2: Measure the effect of the intervention, as compared to a control group, on patient outcomes (HRQOL and interrupted treatment course), and healthcare utilization outcomes (unplanned hospital admissions, unplanned emergency room visits, and unplanned use of intravenous [IV] fluids).

Aim 3: Determine if CG self-efficacy mediates the effect of the intervention on CG anxiety.

Aim 4: Determine if patient illness factors, care demands (hours per week spent caregiving), and patient and CG demographic factors moderate the relationship between the intervention and CG outcomes.

Aim 4a: Examine which social determinants of health (aspects of vulnerability) in caregivers moderate the efficacy of the intervention.

Aim 4b: Explore caregivers' perspectives and experiences regarding the intervention to understand how the intervention should be modified to better serve vulnerable caregivers.

Aim 5: Compare the costs of healthcare utilization (unplanned hospital admission, unplanned emergency room visits, and unplanned use of IV fluids) between the intervention and control groups.

3.0 RESEARCH SUBJECT SELECTION AND ELIGIBILITY

Setting

Radiation Therapy Departments of the Seidman Cancer Center at the University Hospitals main campus, satellite community facilities, and MetroHealth Cancer Center.

Population

The sample will consist of family CGs of individuals with HNC, NSCLC, rectal, anal, and esophageal cancer. In this study, a family CG is defined as an adult who is providing daily assistance and/or emotional support to the individual with cancer as identified by the patient. The sample will be drawn from the population of patients at the Cancer Center. Data obtained from the Cancer Center tumor registry show that 403 adult patients with new diagnoses of HNC, rectal, anal, and esophageal cancer (all stages) and stage III NSCLC cancer were evaluated in 2017. Demographic characteristics were: 62.5% male, 37.5% female, 82.4% White, 16.4% Black, and a mean age of 64 years. Fifty-seven percent underwent radiation therapy.

The extension period will include family CGs and patients recruited from MetroHealth, an academic medical center and Cuyahoga County's safety-net health system. It is located in the City of Cleveland, which is racially and ethnically diverse (49% Black, 40% White, 11.9% Hispanic).

Sampling Procedure and Group Assignment

A convenience sample of family CGs will be used.

Inclusion criteria for patients are: (1) 18 years of age or older. (2) Diagnosis of stage I, II, III

cancers of the rectum and anus, stage I, II, III, IVa esophagus; stage II-III NSCLC (excluding those receiving SBRT due to short treatment course); and stage I – IV A/B head/neck (tongue, gum, oral cavity, nasopharynx, oropharynx, hypopharynx, parotid, or larynx). Stage IV A/B will be allowed for HNC and stage IVa for esophagus as the intent of therapy is curative. (3) Has an identified family CG who is willing to participate.

Inclusion criteria for CGs are: (1) 18 years of age or older; (2) family member or friend of an adult patient described above; and (3) identified by the patient as his/her primary CG, who is providing daily assistance and/or emotional support.

Exclusion criteria are: Patients who do not have a caregiver will be excluded. CGs of patients who are receiving hospice care will be excluded because of the patient's poor prognosis and multiple issues associated with end-of-life care. CGs who are themselves undergoing active cancer treatment will be excluded (hormonal treatment allowed).

Projected Enrollment

We estimate, based on the annual Cancer Registry data, that 131 patients with stage I, II, III rectal, anal, and esophageal cancers; stage III NSCLC; and stage I-IV A/B HNC will be receiving radiation therapy at the three study sites of the Cancer Center. Approximately 10% of these patients will not meet our eligibility criteria (e.g., no family CG), resulting in 118 potential participants annually. Based upon our current pilot study, *Building Family CG Skills Using a Simulation-Based Intervention for Care of Patients with Head and Neck Cancer*, we expect a CG refusal rate of 40%. Therefore, we project to enroll 71 CGs per year or 5 per month. We plan to enroll subjects for 36 months, resulting in an enrollment of 180 subjects over the course of the study. We will allow for a 10% dropout rate, resulting in 162 subjects for the final analysis. The estimated 10% attrition rate is based on a current caregiver intervention study in the Cancer Center, in which the rate is 9.7% (NR015464, [name] PI).

While 40% is a high refusal rate, it is consistent with other intervention studies that aimed to enroll patient-caregiver dyads.^{2,3,90} In addition, the use of incentives has been found to reduce the refusal rate in this CG population, and thus, we will offer a \$100 incentive to all CGs for participation in the study. We will also seek IRB approval to collect additional information from CGs who refuse, including whether the CG is working and/or providing care to other individuals, which were common reasons for refusal in the pilot study. Lastly, we will monitor the refusal rate monthly. If the refusal rate is greater than 40% for more than 4 months, we will consider revising our strategies and seek other sites. We will offer a \$40 incentive to all patients for participation in the study.

For the extension period, with the increased number of study sites we project to enroll 6 caregivers per month. We plan to enroll subjects for an additional 16 months, resulting in 96 subjects over the course of the extension project. We project that the parent study will enroll a total of 148 subjects. Adding the 96 subjects in the extension project will result in a total sample size between the parent study and extension project of 244. With an estimated dropout rate of 12%, the sample for the final analysis will be 214 dyads.

4.0 RESEARCH SUBJECT ENTRY

A convenience sample of family CGs will be used. Potential patients who meet the study inclusion criteria will be identified by the research assistant (RA) through review of the weekly radiation clinic schedules. The diagnosis will be confirmed in the medical record. Based upon pilot work, we have determined the optimal time to approach subjects for inclusion into the study is during the radiation therapy simulation visit, which is approximately 10 days prior to the start of treatment. Consent will be obtained in person.

The patient will be approached by the RA in a private room in the clinic and the study will be explained. The patient will be asked to identify an adult family member or friend who is his/her primary caregiver. We will ask for the patient's approval to talk with the caregiver about the study. *If the caregiver is present in the clinic*, the study will be explained with an opportunity for the caregiver to ask questions. Written consent will be sought from the patient and caregiver. *If the caregiver is not present at that time*, contact information for the caregiver will be obtained and the patient will be asked to give his/her caregiver an information pamphlet about the study. The RA will contact the caregiver within four days to explain the study and to set up an in-person meeting with the caregiver at the clinic. At that

meeting, written consent will be sought from the patient and caregiver.

For the duration of the COVID-19 pandemic, patient and caregiver consent will be obtained remotely by phone or electronically through Redcap whenever possible. If remote consent is not feasible due to the timing of treatment, patient or caregiver factors, or enrollment issues, we will return to our previous in-person consenting protocol, following all hospital guidelines regarding masking and distancing. The remote consenting protocol is as follows: at the new patient visit (NPV) or CT Simulation visit the radiation oncology staff, such as the Nurse Partner, will give the patient our IRB-approved study brochure and two (2) paper copies of the patient and caregiver consent forms. If the NPV is completed via telehealth or there are insufficient clinical notes to assess eligibility, the brochure and consent form will be given to the patient at the in-person CT simulation visit. The brochure contains opt-out information for patients who do not wish to be contacted about the study. Instructions are to call the study office telephone number to opt out of the study. This opt-out is a short time frame of 2 days, and will be pointed out to the patient by the medical staff. If no call or email from the patient is received within 2 days, the study team will call the patient and discuss the research using a script (attached). If the patient gives verbal consent to participate and identifies a caregiver, and the caregiver lives with the patient and is available, we will offer to speak with them together on the phone to answer any questions about the consent.

Secure REDCap links to the patient and caregiver consent forms will be sent to their preferred email addresses. The informed consent process will continue on the telephone and, after questions are answered, the patient and caregiver will electronically sign and date the REDCap consent forms. The consenter will also electronically sign and date the REDCap consent form. The enrollment procedure proceeds with contact information being completed via telephone.

If the patient and/or caregiver do NOT have email or internet access, informed consent will proceed via telephone with the patient and/or caregiver signing paper copies of the consent forms, previously provided by the medical staff. The patient and caregiver will mail the signed forms back to the researcher's office via a study-provided postage-paid envelope (also given at their health care provider visit) and will keep the unsigned copies. The enrollment procedure proceeds with contact information being completed via telephone.

Subjects' capacity to consent will be evaluated by the RA in conjunction with the clinical team. Participants must be cognitively intact, as evidenced by orientation to person, place, and time. They must be able to speak, read, and comprehend English.

All participants are volunteers and non-participation and withdrawal from the study are alternatives to study participation. Patients and caregivers will be told that they may withdraw from the study at any time. There are no risks to non-participation or withdrawal from the study. The RA will explain that participation or non-participation will have no effect on the care that the patient and caregiver will receive from the healthcare team.

For the extension period, caregivers will be offered an additional qualitative interview after completing the intervention. The consent form will give caregivers a choice to opt in and agree to be contacted for an interview. Caregivers randomized to the intervention will be selected for interviews using purposive sampling to select participants with a low score in at least one domain of the social determinants of health. Interviews will be done with 15 caregivers who opted in during the consent process. The interviews will take place after they have completed the intervention.

Once consent is obtained, baseline measures will be collected. All participants will be screened for health literacy using a 4-item Brief Health Literacy Screening Tool (BRIEF), a self-report tool that assesses comprehension to written and verbal health information as well as confidence in filling out medical forms. The research team will employ communication and teaching strategies from AHRQ's Health Literacy Universal Precautions Toolkit⁹⁴ for individuals identified as having limited health literacy.

Once baseline data have been obtained, the Project Director will randomly assign the CG to one of

two groups: control or intervention. Randomization will be done using the minimization stratified randomization technique (QMinim). Minimization is designed to balance pre-identified stratifying covariates across treatment assignments more effectively than simple randomization.⁸⁷⁻⁸⁹ Stratification variables will be CG gender, CG age, and patient cancer type.

The RAs will be blinded to group assignment.

We will not request a waiver for consent documentation from the IRB. We will request partial waiver of HIPAA Authorization due to the need to review the radiation oncology patient schedule to determine potential participants. We will use the following identifiable information in screening for participants in the study: patient name, diagnosis, medical record number, date and time of appointment, and family caregiver name and contact information. The identifiable information will be used only by members of the research team and will be stored on RedCap and UH Box. Identifiers of non-participants will be destroyed when the study is closed to enrollment.

5.0 STUDY DESIGN AND METHODS

5.1 Design/Study Type

This is a 2-group, prospective, randomized controlled design to test the effect of an intervention, as compared to a usual care control group, on CG outcomes, patient outcomes, and healthcare utilization

	Treatment Phase			Posttreatment Survivorship Phase		
	T1 1 st week XRT	3 rd week XRT	T2 End XRT 6 th – 8 th week	2 weeks post XRT	T3 4 weeks post XRT	T4 20 weeks post XRT
Intervention	X	X	X	X _T		
Data	M		M		M	M

Note. XRT = Radiation treatment; X = In-person intervention; X_T = Intervention booster telephone call; M = Measurement.

outcomes during treatment. As shown in Table 2, the intervention involves three in-person, one-on-one teaching sessions with the caregiver during radiation treatments, followed by a telephone booster contact

2 weeks posttreatment. We will collect patient and CG data at baseline (T1), at the end of radiation treatment (T2), and 4 (T3), and 20 weeks (T4) postradiation treatment. We opted to measure outcomes at the completion of radiation treatment (and midintervention) because we want to compare groups when side effects, which develop gradually during radiation therapy, are intense. The timing of measures after treatment was based on our longitudinal descriptive study of patients with HNC and our clinical experience of the trajectory of patient recovery after treatment. The total number of weeks of radiation treatment may vary depending on the specific diagnosis. Therefore, measures taken at T3 and T4 are based on time since completion of radiation treatment. The independent variable is group assignment.

The primary outcome is CG anxiety. Secondary outcomes are CG depression, HRQOL, and fatigue; patient HRQOL and interrupted treatment; and healthcare utilization outcomes. The mediating effect of self-efficacy will be assessed as well as the moderating effects of patient illness factors, care demands, and demographic factors.

The study design during the extension period will not change, except for the addition of a qualitative interview. We will conduct qualitative interviews with a subset of 15 caregivers exploring their perspectives and experiences regarding the intervention.

5.2 Selection of Instruments

We chose measures based on our prior work with caregivers that are psychometrically sound and/or recommended by NIH as common data elements to facilitate cross-study analysis and increase the scientific impact of our study analyses. The instruments can be found in Appendix A.

Caregiver Outcome Variables

The Patient-Reported Outcomes Measurement Information System (PROMIS) will be used to measure caregiver outcome variables. The PROMIS item banks and their short forms were developed and calibrated using item-response theory on large data samples from patients with chronic conditions (including cancer) and the US general population. Reliability and precision of the items in measuring various constructs have been reported by Cella et al.⁹⁵ For each survey, the responses are summed to produce a total raw score, which is converted to a T-score. Higher T-scores represent greater amounts of the construct being measured. Each survey, in our experience, takes approximately two minutes to complete.

Anxiety will be measured with the PROMIS Anxiety Short Form 7a.⁹⁵ This 7-item questionnaire assesses self-reported fear, worry, anxiety, tension, nervousness, and restlessness in the family caregiver over the last 7 days.

Depression will be measured with the PROMIS Depression Short Form 8b.⁹⁵ This 8-item questionnaire assesses caregiver self-reported negative mood (sadness, guilt), views of self (worthlessness), and social cognition (loneliness), as well as decreased positive affect and engagement. It assesses depression over the last 7 days.

HRQOL will be measured using the PROMIS Global Health Scale v.1.0/1.1, a 10-item questionnaire that evaluates global physical health and global mental health.⁹⁵ Caregiver fatigue will be measured with the PROMIS Fatigue Short Form 7a, a 7-item questionnaire that evaluates the self-reported experience of fatigue (frequency, duration, intensity) and the impact of fatigue on daily activities.⁹⁵ It assesses fatigue over the last 7 days.

Caregiver Reaction Assessment will be used at baseline and at time 3 (4 weeks post-XRT) to measure caregiver's reactions to caregiving for family members with an illness. The scale uses a Likert response format.

Patient Outcome Variables

HRQOL in patients will be measured using the disease-specific versions of the FACT-G that include common HRQOL subscales (physical, social, emotional, and functional well-being) plus cancer-specific questions. We will analyze the effect of the intervention on HRQOL across diagnoses using the common FACT subscales and will describe the symptom experience within each diagnostic group using the cancer-specific FACT subscale. Respondent burden is minimal with the FACT surveys, with a completion time on average of 5 to 10 minutes.¹¹⁴ Participants rate their response to each item on a 5-point Likert-type scale. After reverse-scoring negatively worded questions, items are summed. Higher scores indicate better quality of life. Reliability and validity of the FACT-G scale was established in a sample of 854 patients with cancer.¹¹⁵

The Functional Assessment of Cancer Therapy - Colorectal (FACT-C, Version 4) is a 37-item questionnaire that measures self-reported HRQOL in patients with colorectal cancer over the last 7 days.⁹⁶ Good internal consistency, concurrent validity, and sensitivity to change over time were supported.⁹⁶

The Functional Assessment of Cancer Therapy - Head and Neck Scale (FACT-H&N, Version 4) is a 39-item questionnaire that assesses self-reported HRQOL in patients with head and neck cancer over the last 7 days.⁹⁸ Good internal consistency of the FACT-H&N was reported for the total scale ($\alpha = 0.89$).⁹⁸ Convergent versus divergent validity was demonstrated when compared to the Performance Status Scale for Head and Neck Cancer Patients (PSS-HN) in a sample of patients with head and neck cancer receiving various cancer treatments.⁹⁸

The Functional Assessment of Cancer Therapy - Esophageal (FACT-E, Version 4) is a 44-item questionnaire that measures self-reported HRQOL in patients with esophageal cancer over the last 7 days.⁹⁷ Excellent internal consistency of the FACT-E subscales was reported ($\alpha > 0.70$).⁹⁸ Convergent versus divergent validity was demonstrated when compared to the European Organization for the Research and Treatment of Cancer Quality of Life Questionnaire (EORTC QLQ) and esophageal (OES 24) in a sample of patients with esophageal cancer treated with surgery with or without

chemoradiation.⁹⁸

The Functional Assessment of Cancer Therapy - Lung (FACT-L, Version 4) is a 33-item questionnaire that measures self-reported HRQOL in patients with lung cancer over the last 7 days.^{104,105} Psychometric properties of the FACT-L were assessed by Cella et al.¹⁰⁴ in a sample of 116 patients with various types and stages of lung cancer. Internal consistency, construct validity, and sensitivity to change was established.

Interrupted Radiation Treatment Course, defined as the total number of missed treatment days due to patient or caregiver reasons, will be determined from the patient's radiation therapy treatment record. We will also record the duration (number of days) of each episode of absence from treatment.

Healthcare Utilization Outcomes

Healthcare utilization outcomes include unplanned hospital admission, unplanned emergency room visits, and unplanned IV fluid use for treatment of dehydration. We will evaluate the effects of the intervention, as compared to the control group, on these outcomes, as well as describe the costs associated with these outcomes. These outcomes will be measured at T2, T3, and T4.

Mediating Variable

Caregiver self-efficacy for caregiving will be measured with the Caregiver Inventory, a 21-item questionnaire that evaluates the domains of managing medical information, caring for the care recipient, caring for oneself, and managing difficult interactions and emotions.⁹⁹ This scale will be administered at all time points. Participants rate each item on a nine-point scale, ranging from *not at all confident* (1) to *totally confident* (9). Scores are summed, with higher scores indicating greater confidence. Psychometric properties of the Caregiver Inventory were initially reported on data from 133 family caregivers of terminally ill patients.⁹⁹ The Cronbach alpha was 0.91 and validity was supported through correlational analyses with other measures (Perceived Stress Scale and Caregiver Burden Inventory) as well as ratings by caregivers and social workers of caregiving tasks.⁹⁹

In addition, an investigator-constructed survey to measure self-efficacy for specific caregiving skills during radiation therapy will be used for descriptive purposes. Caregivers will rate their confidence in performing specific skills on a 10-point scale.

Covariates

Patient illness factors – stage of cancer, time since diagnosis, treatment type (chemoradiotherapy vs. radiotherapy alone), HPV status (in HNC and anal cancer), use of palliative care, and patient performance status – will be recorded on the enrollment form. Updates for use of palliative care and patient performance status will be noted at T2, T3, and T4. Care demands, defined as hours/week spent caregiving, will be assessed at all time points. Demographic characteristics of both the patient and caregiver will be collected at baseline (T1). Use of mental health interventions (support group participation, social work and/or psychologist Involvement) will be assessed at all time points.

Three additional measures of social determinants of health are health insurance, social support, and financial toxicity. Health insurance will be assessed at baseline for patients and caregivers. Patient health insurance status will be obtained in the medical record, and caregiver insurance status will be obtained through self-report. Financial toxicity will be assessed with the Comprehensive Score for Financial Toxicity measure (COST), a patient-reported outcome measure that includes an 11-item scale and a single summary item of financial hardship. All items are rated on a 5-point Likert scale and lower scores indicate greater financial toxicity. The COST measure has been found to be reliable and valid in assessing caregiver financial toxicity. The 19-item Medical Outcomes Study (MOS) Social Support Survey will be used to measure perceived social support. The survey provides an overall support index score, as well as domain scores for emotional/informational, tangible, positive interaction, and affectionate support. Higher scores indicate greater support. The Ohio Opportunity Index (OOI), which measures health and well-being based on home address,

will be used to describe neighborhood characteristics for caregivers.

Other variables

Intervention dose, defined as the number of intervention sessions the caregiver receives, will be recorded at the completion of the intervention.

Other variables associated with cost analysis

Nurse time for preparation of the simulation and delivery of the intervention (in-person and phone contacts) will be collected prospectively during the study period. CGs will be surveyed at each intervention contact (during radiation weeks 1 and 3, and at the end of radiation treatment) regarding any travel expenses for meetings with the intervention nurse.

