The simulation protocols were modeled after procedures used in nurse education. They contain: (1) CG learning objectives; (2) presimulation preparation, during which the intervention nurse shows the CG the manikin and reviews steps of the procedure; (3) simulation scenarios that are basic and more complex (alternative scenarios) and have a series of critical events that the CG responds to; and (4) a postsimulation debriefing during which the intervention nurse answers questions, assesses the CG's confidence in performing the skills, and provides additional training as necessary. Each simulation manual includes a structured checklist with scenarios, expected CG behaviors, and nurse prompts. Although the simulation training will follow a consistent outline, the content will be tailored to the CG's needs. CGs will have the opportunity to repeat simulations at each session. CGs will be offered a flashlight by the interventionist if they do not have one at home to use for oral assessments. An example of a simulation checklist is shown in Figure 2.

Table 3. Intervention Components

	Session One	Session Two	Session Three
Time	First 10 days of XRT	3 rd – 4 th week of XRT	Completion of XRT
Goal of session	Help CG understand the PT's experience and how to help	Review strategies for current care issues PLUS describe the typical CG experience and how the disease may affect relationship between CG and PT	Review strategies for current issues PLUS discuss common issues and concerns that may arise after cancer treatment
Content			
1. Support (Normalize concerns or experiences, listen, assess & respond to distress)	Assure CG that healthcare team will assist him/her in managing issues. -Assess CG distress & refer to SW if score \geq 5/10 -Identify resources & sources of social support for CG	-Discuss current PT issues or symptoms. -Ask, "What would you like to review today?" -Assess CG distress & refer to SW if score \geq 5/10 -Identify resources and sources of social support for CG	-Discuss current PT issues or symptoms. -Ask, "What would you like to review today?" -Assess CG distress & refer to SW if score \geq 5/10 -Identify resources and sources of social support for CG

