During the extension period, qualitative interviews will be conducted either in-person, by phone, or using UH Zoom based on caregiver preference. The interviewer will follow the interview guide, adding prompts and follow-up questions as appropriate. Interviews will last approximately 30 to 45 minutes. Interviews will be recorded and the data file will be uploaded to UH Box for storage.

Table 4. Study Measures

VARIABLE	INSTRUMENTS	TIME			
		T1	T2	T3	T4
CG Outcomes					
CG Anxiety	Patient Reported Outcomes Measurement Information System (PROMIS) ⁹⁵ Anxiety Short Form 7a	X	X	X	X
CG Depression	PROMIS ⁹⁵ Depression Short Form 8b	X	X	X	X
CG HRQOL	PROMIS ⁹⁵ Global Health Scale v.1.0/1.1	X	X	X	X
CG Fatigue	PROMIS ⁹⁵ Fatigue Short Form 7a	X	X	X	X
Patient Outcomes					
HRQOL	FACT-C, v. 4, ⁹⁶ FACT-E, v. 4, ⁹⁷ FACT-H&N, v. 4, ⁹⁸ and FACT-L, v. 4 ^{104, 105}	X	X	X	X
Interrupted radiation treatment course (total number of missed days from treatments)	Radiation Therapy PT treatment record		X		
Healthcare Utilization Outcomes					
Unplanned hospital admission	Hospital record		X	X	X
Unplanned emergency room visits	Hospital record		X	X	X
Unplanned intravenous fluid use	Hospital record (number of liter bags used)		X	X	X
Cognitive Mediator					
CG self-efficacy for caregiving	CG Inventory ⁹⁹	X	X	X	X
	Investigator-constructed self-efficacy scale for managing side effects & specific skills	X	X	X	X
Potential Moderators (Covariates)					
Patient Illness Factors (Stage; time since diagnosis; treatment type, e.g., concurrent chemotherapy; HPV status in HNC and anal cancer)	PT medical record	X			
Use of palliative care services	PT medical record	X	X	X	X
PT Performance Status	ECOG Performance Status ^{100,101} (patient)	X	X	X	X
Care Demands (hours/week spent caregiving)	Interview questions (CG)	X	X	X	X
Demographic characteristics (race, marital status, employment status, health insurance, socioeconomic status)	Interview questions (CG and PT)	X			
Use of mental health interventions (support group participation, social work and/or psychologist involvement)	Interview questions (CG and PT)	X	X	X	X
Financial toxicity	COST-FACIT (version 2)		X		X
Social support	MOS		X		

Note. PT = Patient; CG = Caregiver; ECOG = Eastern Cooperative Oncology Group; ADLs = Activities of daily living. CG age, CG gender, and PT cancer type will be used in the minimization stratified randomization technique. Number/types of care demands will be collected as descriptive data.

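### Missed treatment days are counted over the whole radiation course, but randomisation has no stated date relative to the first fraction, so days missed before assignment can be scored as outcome

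*Combined protocol and SAP*

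**What the plan says.** **Outcome.** Section 5.2 measures interrupted treatment from the patient's radiation record, "defined as the total number of missed treatment days due to patient or caregiver reasons". Table 4 repeats the total and records it once, at T2. Neither place gives a date from which counting starts.

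**Order of events.** Section 4.0 sets the best time to approach dyads as "during the radiation therapy simulation visit, which is approximately 10 days prior to the start of treatment". It continues: "Once consent is obtained, baseline measures will be collected", and then "Once baseline data have been obtained, the Project Director will randomly assign the CG to one of" two groups. Neither baseline nor randomisation has a date or a window.

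**Schedule.** Section 5.1 equates baseline with T1, and Table 2 labels that column "T1 1 st week XRT", under the treatment phase. Table 3 in Section 5.3 places session 1 in the "First 10 days of XRT". No section requires randomisation before the first fraction.

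**Utilisation.** The Aim 2 analysis in Section 6 uses cumulative counts at T2, T3 and T4 for admissions, emergency visits and IV fluids. No origin is stated. The Aim 5 costs are built on the same events.

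**The concern.** The intervention cannot change a day missed before the caregiver was assigned. If Table 2 describes what happens, some dyads are randomised after radiation has begun, and the outcome as defined then mixes two periods: one the intervention could not reach and one it could.

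This does not bias the test of no effect. Assignment is random, so pre-assignment days have the same expectation in both arms. The cost lies in estimation and power: the rate ratio moves towards 1, and the extra events add noise. Aim 2 has its own power statement for this outcome (80% for a 68% reduction), which is where the loss would show. Whether there is a loss, and how large, depends on how many missed days precede randomisation.

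**Working it through.** **Inputs.** From the Aim 2 power statement in Section 6: control mean 0.29 missed days, 68% reduction (rate ratio 0.32), 81 patients per arm, two-sided 0.05, power 80%. From Section 3.0, Projected Enrollment: 214 dyads now expected in the final analysis, so 214 / 2 = 107 per arm. From Table 2: a course of 6 to 8 weeks. Not in the documents: f, the share of control-arm missed days that fall before randomisation. I treat 0.29 as the whole-course mean and the counts as Poisson without overdispersion.

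**The plan's figure.** With 81 per arm and means 0.29 and 0.29 × 0.32 = 0.0928, the expected totals are 23.5 and 7.5 days. Normal-approximation formulas give power 81.8% (score test) and 77.6% (Wald test on the log rate ratio); the exact conditional binomial test gives 78.8%. The stated 80% reproduces.

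**Dilution.** Each arm has 0.29 × f missed days before assignment. After assignment the control arm has 0.29 × (1 − f) and the intervention arm 0.32 times that. Over the whole course:

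- ratio = f + 0.32 × (1 − f)
- apparent reduction = 0.68 × (1 − f)

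Counting only after randomisation keeps the ratio at 0.32 on a control mean of 0.29 × (1 − f).

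For f = 0.05, the whole-course means are 0.29 and 0.29 × 0.354 = 0.1027, an apparent reduction of 0.68 × 0.95 = 64.6%. The post-randomisation means are 0.2755 and 0.0882. One week of an 8-week or 6-week course, with missed days spread evenly, gives f = 1/8 or 1/6.

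**Power.** For each pair of means I enumerated the two Poisson totals and summed the probability of rejection. Three tests were used: exact conditional, Wald on the log rate ratio (0.5 added to both totals if either is zero), and score. Each cell gives the range over the three.

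| f | Apparent reduction | Whole course, 81/arm | After randomisation, 81/arm | Whole course, 107/arm | After randomisation, 107/arm |
|---|---|---|---|---|---|
| 0 | 68% | 0.79–0.85 | same | 0.90–0.93 | same |
| 0.05 | 64.6% | 0.73–0.79 | 0.76–0.83 | 0.86–0.89 | 0.88–0.91 |
| 1/8 | 59.5% | 0.63–0.70 | 0.72–0.80 | 0.77–0.81 | 0.85–0.89 |
| 1/6 | 56.7% | 0.57–0.65 | 0.70–0.78 | 0.72–0.76 | 0.83–0.88 |

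Test by test, counting from randomisation recovers 3 to 4 points at f = 0.05 with 81 per arm and 2 to 3 points with 107. At f = 1/8 to 1/6 it recovers about 9 to 13 points with 81 and 8 to 11 with 107. It does not recover everything, because fewer days remain to be prevented.

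**The case against.** **A reader might infer that the protocol contradicts itself**, placing baseline and randomisation both 10 days before radiation and in its first week. The text does not support that. The 10 days in Section 4.0 date the approach for consent at the simulation visit, and what follows is only an order of steps. The section also allows for delay: up to four days to contact an absent caregiver and then a separate meeting, or a 2-day opt-out and sometimes mailed forms under remote consent. An approach before radiation and a T1 in week 1 can both be true. What is missing is a randomisation date.

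**A reader might also take the largest power loss as the expected one.** It is an upper bound under Table 2's timing, for three reasons.

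- It needs every dyad to be randomised at the end of week 1. Table 2 puts T1 and session 1 in the same week, and session 1 needs a prior assignment, so randomisation would usually come earlier. The 10-day window for session 1 loosens this but does not make the end of week 1 typical.
- It spreads missed days evenly. Section 5.1 says that side effects build up over the course, so early absences are plausibly fewer than their share of the calendar, although the definition also covers caregiver reasons.
- The lowest figures use 81 per arm, which belongs to the plan for 180 randomised. With 107 per arm, power at f = 0.05 stays above 80% on either count.

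It is also fair that this is one secondary patient outcome, and that Table 4, by leaving T1 blank for missed days and utilisation, hints at counting from baseline. A hint is not a rule, and a total taken from the radiation record points the other way. Days between randomisation and session 1 belong in an intent-to-treat count and are no part of the problem.

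**Conclusion.** The point stands as an undefined counting window. As written, the outcome includes pre-assignment days for any dyad randomised after the first fraction, and nothing in the plan rules such dyads out. The comparison remains valid, and the primary endpoint (caregiver anxiety at T4) is untouched.

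The size depends on f, which the documents do not give. It is nothing if all dyads are randomised before radiation and a few points of power if f is about 5%. At the upper bound, a true 68% reduction appears as 57–60%, with power of 0.57–0.70 at 81 per arm or 0.72–0.81 at 107. These figures rest on Poisson counts, a whole-course control mean of 0.29 and a 68% effect that applies only after assignment. No size is claimed for the utilisation counts; they share the missing start date. Counting from randomisation is a low-cost improvement that does no harm if f turns out to be zero.

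**What to change.** 1. In Sections 4.0 and 5.1 (Table 2), state when T1 and randomisation take place relative to the first fraction.
2. In Section 5.2, Table 4 and the Aim 2 analysis, define missed days as those after the randomisation date. Keep the whole-course total as a descriptive or sensitivity count.
3. Start the admission, emergency-visit and IV-fluid counts for Aims 2 and 5 at the same date.
4. Optionally, use the number of fractions scheduled after randomisation as an exposure offset.

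The cost is wording plus some abstraction. Section 5.2 already takes the outcome from the radiation record and records the length of each absence, but it does not say that dates are captured. The dates of missed days would have to be taken from that record, and the utilisation events dated from the hospital record. No new contact with participants and no change to treatment is involved.
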